5.2 Data processing

Data processing, controls of plausibility and query handling will be carried out by the CRO Winicker Norimed GmbH Medizinische Forschung, Germany. The study database will be created according to the format and content of the eCRF and the CIP. The MedDRA or IMDRF code will be used for coding of adverse events and previous / concomitant diseases.

Clinical Investigation Plan

CIP Reference No.:2018-GI (OEKG) -01. The SAMISEN study - Final Version 03 - Date 28-Jun-2021

6 AMENDMENTS TO THE CIP

CIP amendments or supplements (apart from minor administrative changes) require a written amendment. Amendments must be approved by the EC and the regulatory authorities, if locally applicable, before implementation. A copy of the written approvals will be provided to the investigators.

In the following sections are changes compare to CIP version no. 02 from 23th April 2019:

- Contact addresses and responsibilities
- Trial summary
- Section 1
- Section 3.1.1-3.1.4.
- Section 3.2.1
- Section 3.2.3.
- Section 3.3.
- Section 3.3.1.
- Section 3.3.2.
- Section 3.3.3.
- Section 3.3.5.
- Section 3.3.6.
- Section 3.4.1. -3.4.4.
- Section 4.1.2.
- Section 4.1.3.
- Section 4.2.
- Section 5.2.
- Section 6
- Section 8
- Section 11.2.1.
- Section 11.3.3.
- Section 11.4.
- Section 15

Overall, the ISO version was adapted to ISO14155:2020.

Clinical Investigation Plan

CIP Reference No.:2018-GI (OEKG) -01. The SAMISEN study - Final Version 03 - Date 28-Jun-2021

7 CIP DEVIATIONS

The investigator must not deviate from the procedures described in this CIP.

Under emergency circumstances, deviations from the CIP to protect the rights, safety and well-being of human subjects may proceed without prior approval of the sponsor and the EC. Such deviations must be documented and reported to the sponsor and the EC as soon as possible.

Classifications into minor and major CIP deviations will be performed by the clinical operations manager and statistician at the end of the study.

Major CIP deviations are, but are not restricted to

- Deviation from the in- and exclusion criteria

Clinical Investigation Plan

CIP Reference No.:2018-GI (OEKG) -01. The **SAMISEN** study - Final Version 03 - Date 28-Jun-2021

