3.3.3 Subject Withdrawal or discontinuation

A subject may withdraw his/her consent to participation at any time without explanation and without consequences for further treatment. Moreover, the study participation may be discontinued temporarily or permanently due to one of the following reasons:

1. Any health deterioration of the subject, e.g. ALAT and/or ASAT > 3 times upper limit of normal range,
2. Not acceptable further study participation as determined by the investigator,
3. Occurrence of not tolerable adverse events and/or laboratory value alterations,
4. Technical reasons (change of physician, change of address of subject),
5. Lacking compliance of subject,
6. Pregnancy,
7. Major CIP deviation,
8. Subject lost to follow-up,
9. Death.

If a subject discontinues participation in the study after signing the consent for whatever reason, every effort has to be made to perform an early termination visit in case the ERCP was already conducted. In this case, the same examinations as in the final visit (Visit 4) shall be performed.

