3.3.5 Duration of the Clinical Investigation

The average duration of study participation for subjects completing the study is estimated to be approximately 2 days up to one week. The estimated total study duration for the whole study cohort is approximately one year. The end of study is defined as the date of the database lock.

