3.1 Populations for Analysis

All patients who did not undergo at least one enteroscopy will be considered as dropouts. Dropouts will be excluded from any statistical analyses.

Two different analysis populations will be defined:

The **safety population (SAF)** will consist of all patients who underwent at least one enteroscopy.

The **ITT population (ITT)** will comprise all patients who underwent at least one enteroscopy and did not have any major protocol deviation.

The safety analysis will be performed on the safety population (SAF), which consists of all patients who underwent at least one enteroscopy.

Efficacy analyses will be based on the intent-to-treat (ITT) population, which includes all patients

- who underwent at least one enteroscopy and
- who had not major protocol deviations.

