3.6 Efficacy Analysis

The following efficacy analyses will be performed based on the ITT population:

- The total success rate (the number of therapeutic successes divided by the number of patients who received an enteroscopy) will be computed alongside with its 95% Clopper-Pearson confidence interval.
- The enteroscopy success rate (percentage of procedures with the ability to reach the major papilla or the biliary anastomosis) will be presented alongside its 95% Clopper-Pearson confidence interval.
- The biliary cannulation success rate (percentage of procedures with the ability to selectively cannulate the bile duct and conduct a cholangiography in relation to all cases with enteroscopy success) will be presented alongside its 95% Clopper-Pearson confidence interval.
- The therapeutic (procedural) success rate (percentage of procedures in which the intended treatment could be successfully completed after successful cannulation) will be presented alongside its 95% Clopper-Pearson confidence interval.
- The total procedure time (period in minutes needed to complete the procedure) will be summarized descriptively.
- The enteroscopy time will be summarized descriptively.
- The outcomes for the items in the user feedback for the judgement of handling characteristics and other aspects will be tabulated in frequency tables.

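### Major deviations remove patients from the success rates, but are classified at database lock from an open-ended list with no rule that keeps outcomes from the classifiers

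*Protocol*

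**What the plan says.** Protocol section 7 is the only place that describes how a deviation is graded: "Classifications into minor and major CIP deviations will be performed by the clinical operations manager and statistician at the end of the study". It then gives a list that opens with "Major CIP deviations are, but are not restricted to" and holds one entry, "Deviation from the in- and exclusion criteria". Protocol 3.3.5 fixes the time point: "The end of study is defined as the date of the database lock".

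SAP 3.1 attaches a consequence to the grade. The set labelled ITT is limited to patients who "underwent at least one enteroscopy and did not have any major protocol deviation". SAP 3.6 uses that set for efficacy: "The following efficacy analyses will be performed based on the ITT population". Tables 11.2.4 to 11.2.7, which carry the four success rates, are all planned on it. The set without the deviation rule is kept for safety: "The safety analysis will be performed on the safety population (SAF), which consists of all patients who underwent at least one enteroscopy".

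Protocol 3.3.3 also lists "Major CIP deviation" among the reasons for which a subject's participation may be discontinued during the study.

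**The concern.** A rule that removes patients from an efficacy analysis is harmless only if it is applied without regard to outcome. That is normally secured by fixing the criteria in advance, by keeping outcomes from those who apply them, or by both. Neither is written down here. The criteria are open, and they are applied when the outcome of every patient is already recorded.

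The four success rates and their intervals are the main efficacy result of Phase B, and Protocol 3.2.3 says the Phase B results will be compared with balloon-assisted ERCP and with data from a manual spiral system. If membership of the denominator can depend on success or failure, that comparison can be biased. The planned 95% Clopper-Pearson intervals describe sampling error only and would not show it.

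**Working it through.** **Step 1. The chain of rules**

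- Effect of the grade: a major deviation takes the patient out of the efficacy set (SAP 3.1).
- Where that set is used: all four success rates (SAP 3.6; tables 11.2.4 to 11.2.7). No table gives these rates on the safety population.
- Who grades: the clinical operations manager, a role listed under the sponsor in the study contacts of the Trial Summary, and the statistician (Protocol 7).
- Criteria: an open list with one example (Protocol 7). The SAP adds none; its rules for efficacy (3.4.2) and other rules (3.4.7) are both empty.
- When: end of study, which is database lock (Protocol 7 with 3.3.5).
- When success is recorded: at Visit 2, where the investigator states whether the intervention succeeded (Protocol 3.4.2). The design is open label and single arm (Protocol 3.1.1, 3.1.2).
- Safeguards: Protocol section 16 lists a Data Review Meeting in February 2023, the month of database lock, and the statistical analysis in April 2023. No section ties the classification to that meeting or withholds outcomes from the classifiers.
- Traceability: table 11.1.2 counts the populations and listing 11.5.1 shows membership. Listing 11.5.2 covers eligibility criteria. No table or listing of protocol deviations or reasons for exclusion is planned.

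**Step 2. How large the effect could be**

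The documents give no expected success rate and no expected number of deviations, so there is no figure of the plan to reproduce. The 100 patients in Protocol 3.3.6 are stated not to rest on power. The success counts and the numbers excluded below are assumptions.

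With s successes among n treated patients and k classified as major deviators:

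- all k are failures: rate = s/(n − k), a rise of sk/[n(n − k)]
- all k are successes: rate = (s − k)/(n − k), a fall of k(n − s)/[n(n − k)]

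For n = 100 and s = 75:

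| Excluded | Calculation | Rate | 95% Clopper-Pearson | Shift in points |
|---|---|---|---|---|
| none | 75/100 | 75.0% | 65 to 83% | 0 |
| 5 failures | 75/95 | 78.9% | 69 to 87% | +3.9 |
| 5 successes | 70/95 | 73.7% | 64 to 82% | −1.3 |
| 10 failures | 75/90 | 83.3% | 74 to 90% | +8.3 |
| 10 successes | 65/90 | 72.2% | 62 to 81% | −2.8 |

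Over s = 60 to 90, excluding 5 failures raises the rate by 3.2 points (60/95 = 63.2%) to 4.7 points (90/95 = 94.7%). Excluding 5 successes lowers it by 2.1 points (55/95 = 57.9%) to 0.5 points (85/95 = 89.5%).

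**Step 3. The other three rates**

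SAP 2.4 defines cannulation and therapeutic success on conditional denominators, so the rates do not move together. Excluding a patient in whom the target was not reached raises the total and enteroscopy rates and leaves the other two unchanged. Excluding one who was reached but not cannulated raises the total and cannulation rates and slightly lowers the enteroscopy rate.

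**The case against.** Several points on the other side have force.

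- **Timing.** A reader might infer that exclusions are decided after the results are known. The documents do not say so. Lock and the Data Review Meeting are scheduled two months before the statistical analysis, and first data are listed for May 2023. What stands is narrower: individual outcomes exist at lock and no rule keeps them out of the classification. What each classifier actually sees before lock is not described either.
- **Who classifies.** It is tempting to say that both are sponsor staff. That is documented for the clinical operations manager only; the statistician's employer is not stated in Protocol section 4.
- **Direction.** Nothing in the documents shows that exclusions would favour the device. With more successes than failures, removing failures moves the rate further than removing successes, but that is arithmetic and not evidence of intent.
- **Size.** Subtracting 72.2% from 83.3% would give an 11-point swing, but that sets two opposite extremes of an assumed case against each other. The shift from the all-treated rate is the fair measure.
- **Scope.** The registry adds no procedures beyond routine care and has two inclusion and five exclusion criteria, so major deviations may be few. That stands, although some criteria rest on the investigator's assessment (contraindications, failure of conventional access), so even the named example leaves room for discretion.
- **Exploratory design.** Protocol 4.1.2 plans no efficacy test, so no type I error is at issue. The all-enrolled listings would also let a reader of the full report approximate the all-treated rate. This helps, but no table reports that rate, and exclusions for reasons other than eligibility would be unexplained.
- **Protocol 3.3.3.** Stopping a patient for an evident breach and grading deviations for analysis can be separate acts. The clash with section 7 is a mismatch of wording and does not make the plan unworkable.

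**Conclusion.** The point holds in this form: the plan permits exclusion from the success rates to depend on outcome, because an open list is applied at database lock in an open-label study with outcomes recorded and not withheld. It does not show that this will happen, or in which direction.

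On the assumption of 75 successes in 100 treated patients, five exclusions move the total success rate by at most +3.9 or −1.3 points, and ten by at most +8.3 or −2.8. These are bounds, reached only if every excluded patient has the same outcome. The harm is possible bias in descriptive rates meant for comparison with reference devices. It should be corrected, since the correction is cheap, but it does not undermine an exploratory registry as a whole. It is also separate from whether the set deserves the label ITT: renaming it would leave the discretion untouched.

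**What to change.** 1. Pre-specify the list of major deviations in the SAP and remove the open wording from Protocol section 7. A deviation not on the list does not remove a patient from the efficacy set.
2. Classify and sign off every deviation before database lock, from a listing that omits the success and time fields. If the Data Review Meeting is to serve for this, say so and schedule it before lock.
3. Report the four success rates on every patient who had an enteroscopy (SAF) alongside the deviation-free set. Classification cannot move the SAF rates.
4. Add a listing of each exclusion with its reason.
5. Reconcile Protocol 3.3.3, which uses the major grade as a reason for discontinuation, with the end-of-study classification in section 7.

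The cost is wording in both documents, one outcome-free listing, one exclusion listing and a second set of four rates. The downside is that an unforeseen serious deviation may stay in the main efficacy set and have to be described separately.

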8 DEVICE ACCOUNTABILITY

This study is a post-market study. The PS enteroscopes are CE-marked. Hence from a regulatory perspective strict device accountability is not needed. However, the sponsor will have a list of serial numbers and can track which device was delivered to which study site.

The devices are usually purchased by the site. Olympus will provide devices as loaner equipment to a limited number of sites serving as centers of excellence. Any loaner equipment shall be exclusively used for the examination of study patients. After reaching the agreed quota per site (approximately 25 patients, see also 3.1.4) the device must be returned to Olympus. Details are specified in the Clinical Trial Agreements.

Clinical Investigation Plan

CIP Reference No.:2018-GI (OEKG) -01. The SAMISEN study - Final Version 03 - Date 28-Jun-2021

9 STATEMENT OF COMPLIANCE

9.1 Ethical and Regulatory Aspects

The clinical investigation will be carried out in accordance with the following texts:

- The Declaration of Helsinki (1996)
- Good Clinical Practice (ICH E6) (current version)
- DIN EN ISO 14155:2020

The clinical investigation will not begin until the required approval / favorable opinion from the EC and / or regulatory authority (if applicable) have been obtained. Any additional requirements imposed by the EC or regulatory authority will be followed.

Regulatory reporting responsibilities are specified in the respective Clinical Trial Agreements that also need to be duly signed prior to the first enrollment.

Quality Control and Quality Assurance systems will ensure that the clinical investigation is conducted according to local law and Good Clinical Practices. Olympus Europa SE & Co. KG will follow their own Standardized Operating Procedures covering all aspects of the clinical investigation.

9.2 Patient Coverage

The PowerSpiral medical device is a CE-certified and CE-marked product. Any patient product liability claims will be covered in accordance with the applicable product liability law. Additional patient coverage will be provided by the sponsor if required by national law.

9.3 Retention of Documents

The investigator must conduct the study in compliance with the Medical Devices Act and Good Clinical Practices. The study documents comprise the following:

- Case report forms,
- Data correction/clarification forms,
- Source documents,
- Correspondence between sponsor/CRO and investigator,
- Regulatory documents such as:
 - Signed CIP and any amendments,
 - EC approval and correspondence,
 - Curriculum Vitae of medical personnel (investigators, study nurses, etc.),
 - Subject signed consent forms,
 - Investigator's contract

Clinical Investigation Plan

CIP Reference No.:2018-GI (OEKG) -01. The **SAMISEN** study - Final Version 03 - Date 28-Jun-2021

Source documents for study subjects shall be marked with the CIP Reference number **[2018-GI (OEKG) -01]**.

The CIP, case report forms, correspondence, original informed consent forms, subject identification log with names of the patients and other documents concerning the study must be kept by the investigator in the investigator site file according to local regulations. The safekeeping period is usually 15 years after study close-out.

9.4 Auditing procedures

National or foreign Health authorities may want to inspect your site at any time during or after the study. By participating in this clinical investigation investigators agree to and will grant authorized inspectors access to all original documents, including subject files. If subject files or medical records are stored on a computer system, the investigator (or delegate) shall ensure that data requested by the inspector is printed on paper, dated and signed before handed over to the inspector. Inspectors do not have direct access to the sites computer system.

Also the sponsor (Olympus Europa SE & Co. KG) reserves the right to perform an audit during the active study phase or after study closeout.

Clinical Investigation Plan

CIP Reference No.:2018-GI (OEKG) -01. The SAMISEN study - Final Version 03 - Date 28-Jun-2021

10 INFORMED CONSENT

Before enrolment in the clinical investigation, the investigator must make sure that all eligible subjects are well provided with detailed information, both orally and in writing, about the following points in particular:

- Aims, duration and methods of the clinical investigation.
- Risks, anticipated benefits and potential hazards according to current knowledge.
- That he/she is free to withdraw his/her consent at any time without affecting subsequent treatment or his/her relation to the physician.
- That the clinical research monitors and auditors, Health Authority Inspectors and EC/IRB members may have access to their clinical source data.

Informed consent must be given by a standard written declaration drafted in simple non-technical language. Subjects will also be informed that the data collected during the study will be archived and processed in accordance with local individual data protection law.

The subject must read and understand the contents of this form before signing and dating it. He/she has to be provided with a signed version. No subject may be enrolled in this clinical investigation before giving his/her informed consent in writing.

The investigator will inform all subjects included in the clinical investigation about any new information on the investigational device discovered during the study, in accordance with the recommendations of Olympus Europa SE & Co. KG, the sponsor, and the EC.

The investigator must hold an updated list of all subjects enrolled in the study by recording their subject number. A Subject Identification Log Template will be provided by the sponsor.

Clinical Investigation Plan

CIP Reference No.:2018-GI (OEKG) -01. The SAMISEN study - Final Version 03 - Date 28-Jun-2021

11 ADVERSE EVENTS, ADVERSE DEVICE EFFECTS AND DEVICE DEFICIENCIES

11.1 Definitions (according to ISO 14155:2020)

11.1.1 Adverse event (AE)

The term AE describes any untoward medical occurrence, unintended disease or injury, or untoward clinical signs (including laboratory values) in subjects, users or other persons, whether or not related to the investigational medical device. For subjects this definition includes:

- Events related to the investigational medical device
- Events related to the procedures involved
- For users or other persons, this definition is restricted to events related to investigational medical devices

Note:

A “significant deterioration in laboratory parameters” means an abnormal lab value, which is deemed clinically significant when any of the following conditions is met:

- The abnormality suggests a disease and/or organ toxicity that is new or has worsened from baseline.
- The abnormality is of a degree that requires additional active management, e.g. change of treatment, discontinuation of treatment, close observation, more frequent follow-up assessments, or further diagnostic investigation.

Therefore, a clinically significant deterioration of a lab value is one that indicates a new disease process, worsening of an existing condition, or requires further action(s) to be taken.

11.1.2 Adverse Device Effect (ADE)

An ADE is an adverse event related to the use of an investigational medical device.

Note:

- This definition includes any adverse event resulting from insufficiencies or inadequacies in the instructions for use, the deployment, the implantation, the installation, the operation, or any malfunction of the investigational medical device.
- This definition includes any event that is a result of a use error or intentional misuse.
- This includes medical devices already on the market that are being evaluated for unintended uses, new populations, new materials or design changes.

Clinical Investigation Plan

CIP Reference No.:2018-GI (OEKG) -01. The SAMISEN study - Final Version 03 - Date 28-Jun-2021

11.1.3 Serious Adverse Event / Serious Adverse Device Effect (SAE /SADE)

A SAE/SADE is further specified by the fact that it results or could have resulted in death or severe deterioration of health of a subject, user, or other persons, whether (SADE) or not (SAE) related to the investigational medical device.

The criteria for a Serious Adverse Event (SAE) are the following:

- Led to a death,
- Led to a serious deterioration in health of the subject, that either resulted in:
 - A life-threatening illness or injury, or
 - A permanent impairment of a body structure or a body function, or
 - In-patient or prolonged hospitalization, or
 - In medical or surgical intervention to prevent life threatening illness or injury or permanent impairment to a body structure or a body function,
- Led to fetal distress, fetal death or a congenital abnormality or birth defect.

Note: Planned hospitalization for a pre-existing condition, or a procedure required by the CIP, without serious deterioration in health, is not considered a serious adverse event.

The following points should be taken into account when evaluating the seriousness of an Adverse Event:

- The life-threatening criterion indicates that there was an immediate risk of death at the time of its occurrence. This does not mean that if the adverse event had occurred in a more severe form it would have led to death.
- The following events are not considered to be serious adverse events:
 - An event causing a brief visit to a hospital consultation, an open-door or day hospital.
 - Outpatient treatment in the emergency department although the reason for which this treatment was instituted may be serious.
 - Admission to hospital (more than one night in a hospital bed) including surgical operations planned before or during the study if the condition was present before the study and provided that it does not worsen during the study.

Note:

A state of pregnancy is an exclusion criterion. Hence contraceptive measures must be taken by all subjects of childbearing potential throughout the study. However, if pregnancy is discovered during the study, the study participation must be discontinued immediately and the outcome of the pregnancy must be followed up carefully. Any abnormal outcome of the child or the mother must be documented.

Clinical Investigation Plan

CIP Reference No.:2018-GI (OEKG) -01. The SAMISEN study - Final Version 03 - Date 28-Jun-2021

